#### **6.2.1.2 Dose Priming**

Based on the nonclinical pharmacology of AMG 340, a lower rate of CRS is anticipated than with other T-cell-engaging bispecifics; however, based on the mechanism of action of AMG 340, the most likely DLT to occur is still CRS  $\geq$  grade 3. Cytokine release syndrome will be managed per Principal Investigator discretion and institutional guidelines (a guide for management of CRS is provided in [Table 6-6](#) if institutional guidelines have not been established). Definitions for adverse events, serious adverse events, and DLTs are provided in Section [8.4.6.1.1](#), [8.4.6.1.2](#), and [6.2.1.4.1](#), respectively.

If a grade  $\geq$  3 CRS event occurs in Cohort N (where N represents a Cohort number) during the DLT period, or at the discretion of the DLRT, a dose equal to or less than the dose for Cohort N will be designated as the ‘Priming Dose’ and dose administration in subsequent cohorts (Cohorts N+1 and on) may be modified as follows:

- On Cycle 1 Day 1, subjects will receive the Priming Dose.
- On Cycle 1 Day 8, subjects will receive the full dose corresponding to the cohort in which they have been enrolled.

Note: a second priming dose may be introduced based on emerging data.

If a subject experiences CRS grade  $\geq$  2, or any other grade  $\geq$  2 toxicity after receiving a priming dose that is not unequivocally due to the subject’s underlying malignancy or other extraneous cause, administration of the full dose on cycle 1 day 8 must await approval by the Amgen Medical Monitor(s). At a minimum, CRS must have resolved to

grade  $\leq$  1 before the next is administered. The dose and timing of the full dose for such a subject may be modified at the discretion of the Amgen Medical Monitor and the Investigator; if the subject has their full dose reduced in cycle 1, the subject will be considered DLT-unevaluable and should be replaced. In subsequent cycles, subjects will receive the full dose on day 1.

Following implementation of a priming dose, if administration of the full dose is delayed in cycle 1, the DLT period for that subject should be extended to the same degree (eg, if the full dose is delayed by 4 days, the DLT period will also be extended 4 days). For clarity, treatment-emergent adverse events meeting criteria for a DLT will be treated as a DLT whether they occur after administration of the priming or the full dose.

#### **6.2.1.3 Dose Cohort Stopping Rules**

##### **6.2.1.3.1 Safety**

In Part A, the occurrence of DLTs will drive identification of the MTD and/or RP2D in line with standard practices in an FIH phase 1 study, as outlined in [Figure 1-2](#). If in aggregate  $>$  33% of subjects in Part A experience an unacceptable toxicity, including those that occur outside the DLT window, accrual will be suspended. Enrollment may be re-initiated following a review of all available data by the DLRT and consultation with FDA.

In Part B, accrual to a part will be suspended if  $>$  33% of subjects (ie,  $>$  10 of the planned 40 subjects in Part B) to be enrolled in that part experience unacceptable toxicity. The final decision on suspension of enrollment will be made by the DLRT following review of all available data when the stopping rule threshold is exceeded.

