- During any cycle, if a subject develops an ANC < 500/ $\mu$ L, platelets < 10,000/ $\mu$ L, or a hemoglobin < 6.5 g/dL, blood samples must be collected every 3 days and study treatment withheld. Treatment may resume when ANC returns to  $\geq$  1,000/ $\mu$ L, platelet counts return to  $\geq$  50,000/ $\mu$ L or baseline platelet count levels (in subjects with baseline platelets < 50,000/ $\mu$ L), or hemoglobin returns to  $\geq$  8.0 g/dL.
- AMG 340 should be discontinued in any subject who experiences CRS, TLS, or a non-hematologic treatment-emergent adverse event that meets DLT equivalent criteria until resolution of the toxicity to  $\leq$  grade 1 or baseline; thereafter study drug may be resumed with one dose level reduction with Medical Monitor approval.

Up to 2 dose reductions are allowed to manage toxicity; thereafter toxicity will be deemed 'unacceptable' and the subject will be discontinued from therapy. Assessment schedules and cycles are fixed and should continue regardless of whether a dose is held.

While investigator discretion should be used for subject management with regards to toxicities, guidelines for management of CRS and NT are provided in [Table 6-6](#) and [Table 6-5](#).

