### **9.2 Sample Size Determination**

In Part A, at least 3 subjects are planned for enrollment into each cohort, with the goal of determining the MTD and/or RP2D of AMG 340. Approximately 60 subjects are anticipated in Part A; however, the total number of subjects in Part A will depend upon the occurrence of DLT events and how dose escalation progresses. If the unknown true toxicity rate/DLT rate is 33% in a given cohort, at least 2 DLTs are likely to be observed.

In Part B, up to 40 subjects will be enrolled to further evaluate safety and tolerability, to explore activity of AMG 340 and to evaluate the relationship between PD markers and PK, safety and clinical response. A sample size of 40 subjects was selected to achieve 92% power for testing the hypothesis on ORR at 1-sided alpha of 0.1 using the binomial exact test.

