### **9.4.1 Planned Analyses**

#### **9.4.1.1 Interim Analysis and Early Stopping Guidelines**

Amgen will conduct evaluations of the treatment and outcome of the CRS events treated with siltuximab on an ongoing basis to assess if the threshold for pausing siltuximab treatment has been reached as outlined in the table below. If these stopping rules are met, an ad hoc DLRT will be triggered to review safety data and available PK, PD, and efficacy data. If recommended by DLRT, the use of siltuximab will resume. The stopping rules to trigger an ad hoc DLRT to review siltuximab treatment use a Bayesian approach proposed by Thall, et al (1995); an ad hoc DLRT will be triggered if the posterior probability that the CRS progression to grade 3 rate is greater than 30% is  $> 80\%$  or the posterior probability that the CRS progression to grade 4 rate is greater than 10% is  $> 80\%$ ; or observation of any grade 5 CRS after the event has been treated with

siltuximab. The stopping boundaries presented below assume a prior distribution of Beta (0.6, 1.4) for progression to grade 3 CRS and a prior distribution of Beta (0.2, 1.8) for progression to grade 4 CRS. The evaluations could occur more frequently if necessary to address emerging safety concerns. If the triggered ad hoc DLRT coincide with regular DLRT, they may be combined.

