**Rationale:**

This protocol has been amended to incorporate the following key revisions.

- Updated key safety risks to add thrombocytopenia as a sign of cytokine release syndrome (CRS) based on safety evaluation of the study drug (Table 2-2 and Table 6-6).
- Reduced total number of subjects enrolled in the study. Number of subjects anticipated to be enrolled in part A (dose escalation) was decreased from 100 to 60 subjects to align with the Clinical Development Plan and in part B (dose expansion) was increased from 30 to up to 40 subjects to address regulatory mandate of dose optimization (Sections 1.1, 1.2, 4.1, and 9.2).
- Updated monotherapy [REDACTED]  
[REDACTED]  
[REDACTED]  
[REDACTED], and activity data (Section 4.1.1).

The following updates are considered minor adjustments supporting the continuous effort to align this protocol to other Amgen internal protocols within the prostate portfolio as well as ensuring alignment with AMG 160 and AMG 509.

- Removed electrocardiogram (ECG) from the primary endpoints since statistical analyses of ECG measurements are not planned and the schedule of activities only include ECG assessment during screening (Sections 1.1 and 3).
- Added 6-month landmark radiographic progression-free survival as a secondary endpoint to evaluate clinical activity of study drug (Sections 1.1, 3, 9.4.2.2).
- Clarified definition of 'line/regimen of therapy' as it is a key factor defining the study population (Sections 1.1, 4.1).
- Provided important clarifications for timing of the safety follow-up (SFU) visit and recording of concomitant medication/therapy (Sections 1.3, 6.7.2, 7.1, 8.1.3, Table 1-1).
- Updated survival follow-up/long-term follow-up to specify the surveillance methods and period which extends for up to a maximum of 3 years from the last SFU visit occurring every 6 months (Table 1-1 and Section 8.1.4).
- [REDACTED]  
[REDACTED] ( ) regarding the on-treatment biopsy to guide physicians to discuss the biopsy collection process with subjects and conduct it only if feasible and safe. An additional update was to clarify definition of 'end of infusion' to ensure consistency across all study sites.
- Added a [REDACTED] only for end of treatment visit. Removed a timepoint for [REDACTED]  
[REDACTED] for the safety follow-up visit [REDACTED]
- Updated procedures and schedule for radiologic assessments (Table 1.3 and Section 8.3).
- Updated inclusion criteria (Section 5.1) to:

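### The Part B accrual-suspension rule counts against the planned 40 rather than subjects treated, so it cannot fire before 11 (or 14) are affected; in Part A, pooling across doses dilutes late toxicity at the current dose

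*Protocol*

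**What the plan says.** Protocol 6.2.1.3.1 has one accrual rule for each part.

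- **Part B.** Accrual is suspended when more than "33% of subjects (ie", more than "10 of the planned 40 subjects in Part B) to be enrolled in that part experience unacceptable toxicity". The section adds: "The final decision on suspension of enrollment will be made by the DLRT following review of all available data", with that decision placed at the point where the threshold has been passed. It gives no running proportion, review schedule or minimum number treated.
- **Part A.** If, in aggregate, more than "33% of subjects in Part A experience an unacceptable toxicity, including those that occur outside the DLT window, accrual will be suspended". All dose levels are pooled, including the early single-subject cohorts (Protocol 4.1.1). Restarting needs a review by the Dose Level Review Team (DLRT) and consultation with FDA.

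Other relevant provisions:

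- Protocol 4.1.1 and Table 4-1 give BOIN boundaries per dose cohort, for Part A only.
- SAP 6.3.3 confines the DLT-evaluable set to dose exploration.
- Protocol 6.2.1.4.1 permits, but does not require, review of events after the DLT window.
- Protocol 9.4.1.1 and SAP 7.1 monitor siltuximab use only, with a Bayesian boundary on subjects treated, tabulated every 5.
- Protocol 6.2.1.4 says that after two dose reductions "thereafter toxicity will be deemed 'unacceptable' and the subject will be discontinued from therapy". Section 6.2.1.3.1 does not say whether that meaning applies to the accrual rule.

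**The concern.** An accrual-suspension rule should limit how many people are exposed when a dose proves too toxic. A count fixed against the planned total cannot react to a high early rate: the first ten subjects could all be affected and the printed trigger would stay silent. Part B has no BOIN or DLT boundary to fall back on. Under Protocol 6.2.1.1 it may also open at an RP2D chosen before the MTD is identified.

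The Part A rule is the only mandatory one that counts toxicity after cycle 1. As subjects from low-dose cohorts accumulate in its denominator, it becomes less sensitive to what is happening at the current dose.

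**Working it through.** **The plan's own figures.** 33% of 40 is 13.2, so exceeding 33% takes 14 subjects (35%). Exceeding 10 takes 11, and 11/40 = 27.5%. The count and the percentage do not agree. The count would fit one third of 30 (30/3 = 10). The Amendment 4 rationale records that enrolment "in part B (dose expansion) was increased from 30 to up to 40 subjects", but that origin for the count is an inference.

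**Part B, rule as printed.** With k = 11 or 14 events needed, the chance of suspension by n treated is P(X ≥ k), X ~ Bin(n, p). For n = 10 it is zero at every p, including 100%. With k = 14 it is still zero at n = 13. With k = 11 and n = 20 it is 0.128, 0.412 and 0.755 at p = 40%, 50% and 60%. The mean number treated is close to k/p, capped at 40; for example 11/0.5 = 22 and 14/0.6 = 23.3.

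**Running boundary.** Table 9-1 uses a prior whose mean equals the threshold and whose weight is two subjects (0.6 + 1.4 = 2; 0.6/2 = 30%), and triggers when the posterior probability exceeds 80%. All 16 of its entries reproduce. The same construction at a threshold of 1/3 gives Beta(2/3, 4/3): after x of n, find the smallest x with P(rate > 1/3 | Beta(2/3 + x, 4/3 + n − x)) > 0.80. At n = 5, x = 2 gives 0.576 and x = 3 gives 0.844. At n = 40, x = 16 gives 0.798 and x = 17 gives 0.876. The full boundary is 3/5, 5/10, 7/15, 9/20, 11/25, 13/30, 15/35, 17/40.

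**Comparison.** Exact calculation with 40 subjects, a constant rate, and each outcome known before the next subject is treated. Each cell is the mean number treated at suspension or at 40, then the probability of ever suspending.

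| True rate | 11 count | 14 count | Boundary alone | Boundary + 11 | Boundary + 14 |
|---|---|---|---|---|---|
| 20% | 39.2; 16% | 39.9; 2% | 37.3; 8% | 36.9; 20% | 37.3; 9% |
| 30% | 34.3; 69% | 38.6; 30% | 30.9; 31% | 28.5; 72% | 30.7; 42% |
| 40% | 27.4; 96% | 33.8; 79% | 21.0; 69% | 18.4; 97% | 20.4; 84% |
| 50% | 22.0; >99% | 27.9; 98% | 12.4; 94% | 11.5; >99% | 12.1; 99% |
| 60% | 18.3; >99% | 23.3; >99% | 7.9; >99% | 7.8; >99% | 7.9; >99% |

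The boundary alone stops earlier, but at a true 40% it suspends less often than either count, because it ends at 17 of 40. It cannot replace the count.

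**Part A dilution.** Protocol 2.2.4.3 reports 23 treated and one subject with DLT events at the March 2022 cutoff. Assume that one subject is the only one counted as affected. Find the smallest k with (1 + k)/(23 + k) > 0.33: k = 9 gives 10/32 = 31.3% and k = 10 gives 11/33 = 33.3%, so ten consecutive affected subjects are needed. With 0, 2 or 5 already affected the answer is 12 (12/35), 9 (11/32) or 4 (9/27). From 1 of 23, 3 of 3 at a new dose gives 4/26 = 15.4% overall, and 6 of 6 gives 7/29 = 24.1%.

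**A per-dose 33% rule in Part A.** 1/3 = 33.3% exceeds 33%, so one event in a minimum-size cohort would suspend accrual. At BOIN's 30% target that has probability 1 − 0.7³ = 66%. Table 4-1 de-escalates only at 2 of 3 or 3 of 6.

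**The case against.** The strongest reply is that these are mandatory triggers, not the whole of safety oversight. Dose level review meetings also cover expanded cohorts and safety signals (Protocol 11.3), and the sponsor may stop the study for safety (Study and Site Closure). Part B is dosed at or below the MTD, or at the RP2D, so true rates of 50% to 60% would be about twice the BOIN target. At 40% the gain is smaller. All this is fair. A reader might infer that Part B would go on enrolling whatever happened, and the documents do not support that. What stands is that those safeguards are discretionary, and that the one quantitative rule cannot respond early.

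For Part A, a reader might infer that late toxicity is hidden or that current-dose toxicity is unprotected. Neither follows. BOIN governs DLTs in the window at each dose, late events may be considered (6.2.1.4.1), and escalation decisions also weigh clinically significant toxicity (6.2.1.1). Nor is the Part A denominator the planned 60, so the rule could have fired while few had been treated.

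The Part A illustration also depends on what counts as unacceptable. If the 8 of 23 with grade 3 or higher events counted, the aggregate would be 34.8% and already over the line.

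**Conclusion.** The Part B point holds under either printed threshold and whatever unacceptable toxicity means: the trigger needs 11 or 14 affected subjects regardless of how few have been treated. Relative to a running boundary with the count kept as a cap, the printed rule treats on average about 9 to 13 more subjects at a true 40%, 10 to 16 more at 50%, and 11 to 15 more at 60%. These sizes assume immediate ascertainment. If unacceptable toxicity means toxicity persisting after two dose reductions, events would mature over several cycles and every version would react later.

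The conflict between 33% and more than 10 of 40 is a separate defect in the same sentence. The documents do not show which was intended.

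The Part A point is narrower. The aggregate rule is diluted by earlier low-dose subjects, and this matters mainly for toxicity outside the DLT window. Its size depends on an assumed number already affected. It does not justify replacing the aggregate rule with a bare per-dose percentage.

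**What to change.** **Part B.** Reconcile the two printed thresholds. Add a boundary on subjects treated, reviewed after every 5, for example the 3/5 to 17/40 series above, and keep the reconciled count as a mandatory cap. State what counts as unacceptable toxicity and the follow-up a subject needs before being counted.

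**Part A.** Keep the aggregate rule. If a per-dose rule for late toxicity is wanted, make it an addition that sets a minimum number treated, is consistent with Table 4-1, and says to which dose an event is attributed when a subject has been escalated under 6.2.1.1.

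**Cost.** A short amendment to 6.2.1.3.1 and at most eight scheduled Part B reviews (40/5). The chance of a pause for review at a true 20% rises from 16% to about 20% (11 count) or from 2% to about 9% (14 count). At a true 30% it rises from 69% to 72%, or from 30% to 42%. A pause leads to DLRT review, not automatic closure.

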### **Number of Subjects**

The total number of subjects enrolled in both parts of the study is anticipated to be approximately 100 subjects (up to 60 subjects in Part A [monotherapy dose escalation] and up to 40 subjects in Part B [monotherapy dose expansion]) at sites in the US with a potential expansion to sites in Europe and the Asia-Pacific (APAC) region.

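### The Part B suspension rule equates > 33% with > 10 of 40 subjects, but > 33% of 40 means 14 or more and > 10 means 11 or more

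*Protocol*

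**What the plan says.** Protocol Section 6.2.1.3.1 (Safety, under Dose Cohort Stopping Rules) gives one suspension rule for each part.

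- **Part A:** accrual is suspended if, in aggregate, more than "33% of subjects in Part A experience an unacceptable toxicity, including those that occur outside the DLT window". No count is attached.
- **Part B:** accrual is suspended if more than "33% of subjects (ie", more than "10 of the planned 40 subjects in Part B) to be enrolled in that part experience unacceptable toxicity". The parenthesis offers the count as another way of stating the percentage.
- **Who decides:** "The final decision on suspension of enrollment will be made by the DLRT following review of all available data", and this step follows once the threshold has been exceeded.

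The denominator of 40 is the current Part B size. The synopsis has "up to 40 subjects in Part B [monotherapy dose expansion", and Section 9.2 says "In Part B, up to 40 subjects will be enrolled to further evaluate safety and tolerability". SAP Section 7.1, on interim analysis and early stopping, covers only siltuximab and does not restate the Part B rule.

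**The concern.** A percentage and a count joined by *ie* should give the same decision for every possible result. These two do not, because 10 is a quarter of 40, not a third.

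This is the only numeric AMG 340 toxicity threshold in either document for suspending Part B accrual. The BOIN boundaries govern Part A, and SAP Section 6.3.3 restricts the DLT set to the dose-exploration part. If 11, 12 or 13 subjects were affected, one member of the DLRT could correctly say the rule had been met and another could correctly say it had not. A rule in that state can be neither followed nor audited.

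**Working it through.** **Inputs**

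- Percentage threshold: > 33% (Protocol 6.2.1.3.1)
- Count threshold: > 10 (same sentence)
- Denominator: the planned 40 (same sentence; agrees with the synopsis and Sections 4.1.2 and 9.2)

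**Step 1. Try to reproduce the stated count.** The first count that exceeds a fraction *t* of *N* is the smallest whole number *x* with *x*/*N* > *t*.

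- *t* = 0.33: 0.33 × 40 = 13.2, so *x* = 14
- *t* = 1/3: 40/3 = 13.33, so *x* = 14

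The stated figure of > 10, that is 11 or more, is not reproduced.

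**Step 2. Compare the two forms at each count.**

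| Affected of 40 | Percent | > 33% met? | > 10 met? |
|---|---|---|---|
| 10 | 25.0 | no | no |
| 11 | 27.5 | no | yes |
| 12 | 30.0 | no | yes |
| 13 | 32.5 | no | yes |
| 14 | 35.0 | yes | yes |

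They disagree at exactly 11, 12 and 13.

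**Step 3. Look for a reading that reconciles them.** The first count above 33% is 11 only when *N* is 31, 32 or 33; above one third, only when *N* is 30, 31 or 32. Rounding does not bring 40 into either range. A running denominator (subjects treated so far) is not what the sentence says, since it fixes the denominator as the planned 40.

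**Step 4. Likely origin.** The Amendment 4 rationale records that Part B "was increased from 30 to up to 40 subjects". One third of 30 is 10, so the count probably survived from the smaller size. This is an inference, and the contradiction in the current text does not depend on it.

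**Step 5. Size.** The documents give no Part B rate of unacceptable toxicity, so the true rate *p* below is assumed. With *X* the number affected among 40 independent subjects, P(*X* ≥ *k*) = Σ C(40, *x*) *p*^*x* (1 − *p*)^(40 − *x*), summed from *x* = *k* to 40.

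| Assumed *p* | P(*X* ≥ 11) | P(*X* ≥ 14) | P(11 ≤ *X* ≤ 13) |
|---|---|---|---|
| 10% | 0.0015 | < 0.0001 | 0.0015 |
| 15% | 0.030 | 0.001 | 0.029 |
| 20% | 0.161 | 0.019 | 0.141 |
| 25% | 0.416 | 0.103 | 0.313 |
| 30% | 0.691 | 0.297 | 0.395 |
| 33% | 0.817 | 0.452 | 0.365 |

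At 5% the last column is below 0.00001. All these are totals after 40 subjects. Crossing 11 while a quarter of accrual remains, that is within the first 30 subjects, is less likely: 2.6% at *p* = 20%, 27% at 30% and 40% at 33%.

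**Step 6. Earliest possible trigger.** Because the denominator is the planned 40, the rule cannot be met before the 11th subject under the count, or the 14th under the percentage.

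**The case against.** Nobody can rescue the arithmetic, so the case on the other side is about consequence.

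- **There is a cautious reading.** The count is the more concrete form, names its own denominator and is stricter. Anyone following it reviews sooner, not later. This is true, but nothing in the text gives the count priority. The Part A rule uses the same 33% with no count, which suggests the percentage was intended.
- **The DLRT has discretion.** It makes the final decision, and Protocol Section 11.3 has dose level review meetings that also cover expanded cohorts and the application of stopping rules. This limits the harm. However, the DLRT's decision under this rule comes once the threshold is exceeded, so the disputed number determines whether that step is triggered.
- **The ambiguous zone may rarely be reached.** Section 6.2.1.4 calls toxicity unacceptable once two dose reductions have been used. That is a subject-level rule with no cross-reference from the suspension rule, but it is the nearest thing to a definition. In Section 2.2.4.3, 1 of 23 treated subjects (4.3%) stopped AMG 340 for an adverse event and one subject had DLT events. At rates like these the conflict almost never arises. On the other hand, 8 of 23 (34.8%) had an event of grade 3 or higher, so a broader definition reaches the upper rows of the table. The plan does not say which events count for this rule.
- **End-of-enrolment totals overstate the effect on accrual.** This is correct; the 30-subject figures in the working show by how much.

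These points bear on how much the error matters. None of them says which threshold applies.

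**Conclusion.** The concern holds. The Part B rule is wrong as written: for 40 subjects, > 33% requires 14 or more affected and > 10 requires 11 or more, and no rounding, choice between 33% and one third, or permitted denominator makes them agree. The SAP does not resolve it.

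The practical size depends on a rate the documents do not give. The chance of finishing Part B in the disputed range runs from practically nil at a true rate of 5% to about 39% at 30%, assuming independent subjects and full enrolment of 40. No efficacy or primary-endpoint analysis is affected. Even so, a numeric safety trigger should have one value, so this needs correcting before Part B relies on it.

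**What to change.** State one matched pair in Section 6.2.1.3.1, with the sponsor confirming which was intended:

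- more than 33%, that is, 14 or more of the planned 40; or
- more than 25%, that is, 11 or more of the planned 40.

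Until that is confirmed, apply the stricter count of 11 or more.

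The edit is one figure, but it changes a stopping rule. It therefore goes through a protocol amendment and IRB/IEC submission under Section 11.3, and could travel with the next planned amendment. Choosing 14 tolerates up to three more affected subjects before review (14 − 11 = 3). Choosing 11 brings more reviews: at an assumed 30% rate the chance of crossing within 40 subjects is 69% rather than 30%.

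Two further changes would help but are not needed to remove the contradiction. One is to say which events count as unacceptable toxicity for this rule, and whether the use of that word in Section 6.2.1.4 applies. The other is to express the threshold against subjects treated so far with a minimum number, so that it can act earlier, at the price of some extra DLRT reviews.
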